# 578 **6.2.3 Hypoglycemic Events**

- 579 Hypoglycemia is only reportable as an adverse event when one of the following criteria is met:
- A hypoglycemic event occurred meeting the following definition of severe hypoglycemia: the 580 event required assistance of another person due to altered consciousness, and required another 581 582 person to actively administer carbohydrate, glucagon, or other resuscitative actions. This means that the participant was impaired cognitively to the point that he/she was unable to treat 583 himself/herself, was unable to verbalize his/ her needs, was incoherent, disoriented, and/or 584 combative, or experienced seizure or loss of consciousness. These episodes may be associated 585 with sufficient neuroglycopenia to induce seizure or loss of consciousness. If glucose 586 measurements are not available during such an event, neurological recovery attributable to the 587 restoration of glucose to normal is considered sufficient evidence that the event was induced by a 588 low glucose concentration. 589
- Evaluation or treatment was obtained at a health care provider facility for an acute event
   involving hypoglycemia, or the participant contacted the site and received guidance following
   the occurrence of an acute event involving hypoglycemia
- Hypoglycemia occurred that was associated with an ADE as defined in section 6.2.1
- Study device discontinued due to hypoglycemia
- 595 When a severe hypoglycemia event occurs (as defined above), a Hypoglycemia CRF should be completed 596 in addition to the Adverse Event CRF. Severe hypoglycemia events should be considered serious adverse 597 events with respect to reporting requirements. When a severe hypoglycemia event occurs during use of a 598 study device, it generally will be considered unrelated to the device (per section 6.2.1) if the device
- functioned as intended and there does not appear to be a flaw in how the device is intended to function.
- 600 6.2.4 Hyperglycemic/Ketotic Events
- 601 Hyperglycemia or ketosis is only reportable as an adverse event when one of the following criteria is met:
- evaluation or treatment was obtained at a health care provider facility for an acute event involving
   hyperglycemia or ketosis, or the participant contacted the site and received guidance on how to
   manage the hyperglycemia/ketosis

- the event involved DKA, as defined by the Diabetes Control and Complications Trial (DCCT) and
   described below
- 607 Symptoms such as polyuria, polydipsia, nausea, or vomiting;
- 608 Serum ketones >1.5 mmol/L or large/moderate urine ketones;
- $\circ$  Either arterial blood pH <7.30 or venous pH <7.24 or serum bicarbonate (or CO2) <15; and
- 610 Treatment provided in a health care facility
- Hyperglycemia occurred that was associated with an ADE as defined in section 6.2.1
- Study device discontinued due to hyperglycemia
- 613 When a hyperglycemia/ketotic event qualifies as an SAE as defined in section 6.2.1, a
- 614 Hyperglycemia/DKA CRF should be completed in addition to the Adverse Event CRF. Events meeting
- DKA criteria should be considered serious adverse events with respect to reporting requirements.
- 616 Hyperglycemia events not meeting criteria for DKA generally will not be considered serious adverse
- 617 events unless one of the SAE criteria in section 6.2.1 is met.
- 618 When a hyperglycemia/DKA event occurs during use of a study device, it generally will be considered
- 619 unrelated to the device (per section 6.2.1) if the device functioned as intended and there does not appear
- 620 to be a flaw in how the device is intended to function.
- 621

# 6.2.5 Relationship of Adverse Event to Study Device or Study Procedure

- The site investigator will assess the relationship of any adverse event to be related or unrelated by
- determining if there is a reasonable possibility that the adverse event may have been caused by the study
- 624 device or a study procedure. The Medical Monitor also will make this assessment, which may or may not
- agree with that of the site investigator. Reporting requirements will be based on the Medical Monitor's
- 626 assessment as the Sponsor's representative.
- To ensure consistency of adverse event causality assessments, investigators should apply the following general guideline when determining whether an adverse event is related:
- **Unrelated:** The AE is clearly not related to a study device/procedure and a likely alternative etiology exists such as an underlying disease, environmental or toxic factors or other therapy.
- Unlikely Related: The AE does not follow a reasonable temporal sequence during or after use of study device/procedure and a more likely alternative etiology exists such as an underlying disease, environmental or toxic factors, or other therapy.
- Possibly Related: The AE occurred in a reasonable time during or after use of study device or a study procedure; but could be related to another factor such as an underlying disease,
   environmental or toxic factors, or other therapy; and there is a possible, though weak, scientific basis for establishing a causal association between the AE and the study device.
- Probably Related: The AE occurred in a reasonable time during or after use of study device or a study procedure; is unlikely to be related to another factor such as an underlying disease, environmental or toxic factors, or other therapy; and there is a plausible, though not strong, scientific basis for establishing a causal association between the AE and the study device.
- Definitely Related: The AE occurred in a reasonable time during or after use of study device or a study procedure; cannot be explained by another factor such as an underlying disease, environmental or toxic factors, or therapy; and there is a strong scientific basis for establishing a causal association between the AE and the study device.

646 Events determined to be *Possibly Related*, *Probably Related*, or *Definitely Related* will be considered to

647 meet the *reasonable possibility* causality standard for relatedness and necessitate reporting as required 648 (see 21 CFR 312.32 for more information).

6.2.6 Severity (Intensity) of Adverse Events

The severity (intensity) of an adverse event will be rated on a three-point scale: (1) mild, (2) moderate, or
(3) severe. A severity assessment is a clinical determination of the intensity of an event. Thus, a severe
adverse event is not necessarily serious. For example, itching for several days may be rated as severe, but

653 may not be clinically serious.

649

- MILD: Usually transient, requires no special treatment, and does not interfere with the participant's daily activities.
- MODERATE: Usually causes a low level of inconvenience, discomfort or concern to the
   participant and may interfere with daily activities, but is usually ameliorated by simple
   therapeutic measures and participant is able to continue in study.
- SEVERE: Interrupts a participant's usual daily activities, causes severe discomfort, may cause discontinuation of study device, and generally requires systemic drug therapy or other treatment.
- 661 6.2.7 Expectedness

662 For a serious adverse event that is considered possibly related to study device/procedure, the Medical

- Monitor will classify the event as unexpected if the nature, severity, or frequency of the event is not consistent with the risk information previously described in the approved labelling of the Control-IQ study pump.
- 666 **6.2.8 Coding o**

# 6.2.8 Coding of Adverse Events

Adverse events will be coded using the MedDRA dictionary. To facilitate coding, the site will enter a preliminary MedDRA code which the Medical Monitor may accept or change (the Medical Monitor's MedDRA coding will be used for all reporting). The Medical Monitor will review the investigator's assessment of causality and may agree or disagree. Both the investigator's and Medical Monitor's assessments will be recorded. The Medical Monitor will have the final say in determining the causality as well as whether an event is classified as a serious adverse event and/or an unanticipated adverse device effect.

674

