# **6.2.1 Definitions**

503 Adverse Event (AE): Any untoward medical occurrence (including laboratory findings) associated with 504 study procedures, the use of a device, biologic, or drug in humans, including any comparator used, 505 whether or not the event is considered related (i.e., irrespective of the relationship between the adverse 506 event and the device(s) under investigation).

507 To further clarify, an adverse event is any unintended disease or injury, or untoward clinically significant 508 clinical sign (including abnormal laboratory findings) in a research participant that manifests while in the

509 study if it was not present before enrolling in the study, or if it was present before enrolling, it has

510 increased in severity, frequency or type since enrolling in the study. For this purpose, a participant is

511 considered enrolled once the participant has signed the consent form. Reportable AEs for this protocol are

- 512 defined in section 6.2.2.
  - 513 Serious Adverse Event (SAE): Any untoward medical occurrence that results in any of the following 514 outcomes:
  - 515 Death.
  - A life-threatening adverse event; (a non-life-threatening event which, had it been more severe, 517 might have become life-threatening, is not necessarily considered a serious adverse event).
  - Inpatient hospitalization or prolongation of existing hospitalization.
  - A persistent or significant disability/incapacity or substantial disruption of the ability to conduct 520 normal life functions.

• A congenital anomaly or birth defect.

522 An important medical event that may not result in death, be life-threatening, or require hospitalization

- 523 may be considered serious when, based upon appropriate medical judgment, they may jeopardize the
- 524 patient or subject and may require medical and surgical intervention to prevent one of the outcomes listed
- 525 in this definition. Note: If either the Sponsor or investigator believes that the event is serious, the event
- 526 must be considered serious and evaluated by the Sponsor for expedited reporting. See 21 CFR 312 for 527 more information.
- 528 Unanticipated Adverse Device Effect (UADE): Any serious adverse effect on health or safety or any life-
- 529 threatening problem or death caused by, or associated with a device, if that effect, problem, or death was
- not previously identified in nature, severity, or degree of incidence in the investigational plan or

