# 743 **6.5 Safety Oversight**

The study Medical Monitor will review all adverse events and adverse device events that are reported

during the study. SAEs typically will be reviewed within twenty-four (24) hours of reporting. Other AEs

typically will be reviewed on a weekly basis. Additionally, the Medical Monitor will review compiled

safety data at periodic intervals (generally timed to the review of compiled safety data by the DSMB).

- 748 The Protocol Chair/Coordinating Investigator will be informed of all cases of severe hypoglycemia and
- 749 DKA and the Medical Monitor's assessment of relationship to the study device; and informed of all 750 reported device issues.
- A Data and Safety Monitoring Board (DSMB) will be informed of all cases of severe hypoglycemia and
- diabetic ketoacidosis irrespective of device relationship, all device-related SAEs, and all UADEs at the
- time that they occur during the study and will review compiled safety data at periodic intervals. The

DSMB also will be informed of any ADEs not meeting criteria for a UADE if the Medical Monitor

requests the DSMB review. The DSMB can request modifications to the study protocol or suspension or

outright stoppage of the study if deemed necessary based on the totality of safety data available. Details

- regarding DSMB review will be documented in a separate DSMB document.
- 758 **6.6 Stopping Criteria**

# 759

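### Protocol sections 6.2.1 and 6.2.8 contradict each other on who decides that an adverse event is serious, and neither the protocol nor the SAP says whose assessment fills the safety tables

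*Protocol*

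**What the plan says.** On seriousness, the definition of an SAE in Protocol 6.2.1 carries a note: "If either the Sponsor or investigator believes that the event is serious, the event" "must be considered serious and evaluated by the Sponsor for expedited reporting". One party's belief is enough, and the consequence is mandatory.

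Protocol 6.2.8 then states: "The Medical Monitor will have the final say in determining the causality as well as whether an event is classified as a serious" adverse event, a UADE, or both. The same section says: "Both the investigator's and Medical Monitor's assessments will be recorded". That sentence directly follows one about causality.

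On causality, Protocol 6.2.5 has the site investigator and the Medical Monitor each assess relatedness, and continues: "Reporting requirements will be based on the Medical Monitor's" "assessment as the Sponsor's representative".

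Protocol 6.5 has the DSMB told, as events occur, of every case of severe hypoglycemia and "diabetic ketoacidosis irrespective of device relationship, all device-related SAEs, and all UADEs at the" time they occur. ADEs that are not UADEs go to the DSMB only if the Medical Monitor asks for its review.

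Protocol 8.4.1 and SAP 5.1 list, among the safety endpoints, other SAEs, ADEs, SADEs, UADEs and a related/not-related split of reportable hyperglycemia events. Protocol 8.13 and SAP section 7 say that the safety endpoints will be tabulated and reportable events listed. Neither says whose seriousness or causality assessment is used.

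**The concern.** The primary outcomes of this single-arm study in children aged 2 to under 6 are safety outcomes (Protocol 8.2), and the protocol itself calls it a significant-risk device study (1.4). A reader of the final tables needs to know what made an event count as serious. As written, two people following the protocol faithfully could classify the same event differently: one would keep it serious because the investigator said so, the other would drop it because the Medical Monitor ruled otherwise. The person with the final say represents the Sponsor, so a resolution left to practice would not look independent.

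More than a table row depends on the label. It decides whether a device-related event reaches the DSMB at once and, under Protocol 6.2.9, whether a related event is still followed after the participant finishes. With no formal stopping rules (8.18), the DSMB acts on what it is shown.

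**Working it through.** No arithmetic applies, and the plan states no figure on this point. The check compares the two rules case by case and then traces what depends on the answer.

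**Step 1: seriousness under each rule.** The Medical Monitor is taken to speak for the Sponsor, as in 6.2.5.

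| Investigator | Medical Monitor | Under 6.2.1 | Under 6.2.8 |
|---|---|---|---|
| serious | serious | serious | serious |
| not serious | not serious | not serious | not serious |
| not serious | serious | serious | serious |
| serious | not serious | **serious** | **not serious** |

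The rules differ in one case of four. In that case 6.2.8 gives the lower classification, so relative to 6.2.1 the difference can only run downward.

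**Step 2: causality.** The note in 6.2.1 concerns seriousness only. Sections 6.2.5 and 6.2.8 say the same thing about relatedness: both parties assess it, and the Medical Monitor's assessment governs. There is no conflict.

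**Step 3: what changes if the investigator's call of serious is overruled.**

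- Other SAEs: the event can leave the count.
- SADE: the event can leave the count if it is device-related.
- UADE: possibly. The definition in 6.2.1 turns largely on seriousness, but UADE status has its own final say in 6.2.8 and no either-party rule.
- DSMB notice (6.5): a device-related event that is no longer an SAE or UADE loses immediate notice, unless it is severe hypoglycemia or DKA or the Medical Monitor requests review.
- Follow-up (6.2.9): only UADEs and related SAEs are followed to resolution or stability after the study. For other events data collection stops when the participant completes.

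**Step 4: what does not change.**

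- Severe hypoglycemia and DKA are defined by clinical criteria and are to be treated as SAEs for reporting (6.2.3, 6.2.4). Their counts and rates stand.
- Ketone days and the CGM percentages below 54 and above 250 mg/dL do not use the label.
- The related/not-related split of hyperglycemia events depends on causality, not seriousness, and both rows are tabulated.
- The any-AE rate and the event listing change only if an event was reportable solely because it was called an SAE. Section 6.2.2 gives several other routes, such as an emergency department visit or discontinuation of a study device.

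**Step 5: which assessment fills the tables.** Protocol 8.13 and SAP section 7 are silent. That the tables would follow 6.2.8 is an inference from its wording.

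**The case against.** The strongest defence is that the two sections do different jobs: the 6.2.1 note ends in evaluation for expedited reporting, a handling step, while 6.2.8 settles the final classification. That reading is possible, but it is not written, and the duty to consider the event serious in 6.2.1 carries no condition. Clarification is still needed.

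Safeguards also exist. The DSMB hears of every severe hypoglycemia and DKA event whatever its relationship to the device, and reviews compiled safety data periodically. Investigators report possibly related SAEs to the Sponsor within 24 hours, and sites under the JCHR IRB report serious related events to it within seven calendar days (6.4). Every reportable event is listed. Several SAE criteria, such as death and hospitalization, leave little room for disagreement; discretion lies mainly with important medical events. All this stands and limits the reach of the problem. It does not say which rule applies when the two parties disagree.

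Four stronger readings are tempting, and the documents do not support them.

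- **The contradiction extends to causality.** It does not (step 2). Counting an event as related when either party says so would be a new policy, not a reconciliation.
- **The Sponsor's representative can remove events from the primary safety results.** Severe hypoglycemia, DKA and the CGM endpoints cannot be removed by a seriousness ruling, and removal from the other tables is inferred, not stated.
- **The counts are biased downward.** Section 6.2.8 lets the Medical Monitor raise a classification as well as lower it. The difference is downward only in comparison with 6.2.1, and no net bias is shown.
- **Each reclassified event moves a rate by about 22 per 100 person-years.** The arithmetic is right: 30 × 56 / 365.25 = 4.60 person-years, and 100 / 4.60 = 21.7. But other SAEs, ADEs, SADEs and UADEs are not specified as rates, and the safety window in 8.5 covers all enrolled participants from enrollment to the post-study contact or day 71 after initiation, so 4.60 is not its denominator.

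**Conclusion.** The plan is wrong as written on one specific point: who decides seriousness when the investigator says yes and the Medical Monitor says no. The conflict is in the text and rests on no outside figure.

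Its size is one event per disagreement. The documents give no expected number of serious events or of disagreements, so no expected effect can be computed. With about 30 participants, a single reclassification could change an entry for other SAEs or SADEs from one to zero, withhold immediate DSMB notice, or end follow-up of a related event.

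The consequence for the tables assumes that they would follow 6.2.8, which neither document states; that silence is a second, smaller gap. The correction should be made because it is specific and nearly free, but it does not call the CGM hypotheses or the severe hypoglycemia and DKA results into question.

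**What to change.** 1. Amend Protocol 6.2.8 so that the Medical Monitor's final say on seriousness is subject to the either-party rule in 6.2.1: an event that the investigator calls serious stays serious.
2. State explicitly that both parties' seriousness judgements are recorded. The present sentence on recording follows one about causality and does not clearly cover seriousness, so check that the AE form captures both.
3. In Protocol 8.13 and SAP section 7, state that SAE and SADE counts use the 6.2.1 rule for seriousness, and name whose causality assessment defines the ADE, SADE and UADE counts. Keeping the Medical Monitor's causality assessment would be consistent with 6.2.5; the need is to say so.
4. List for the DSMB the events on which the investigator and the Medical Monitor disagree about seriousness or causality.

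The cost is some wording in both documents, one extra listing, a data field if the seriousness judgements are not already captured separately, and counts that may look slightly less favourable.

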# 6.2.9 Outcome of Adverse Events

- The outcome of each reportable adverse event will be classified by the investigator as follows:
- 676 RECOVERED/RESOLVED (COMPLETE RECOVERY) The participant recovered from the
   677 AE/SAE without sequelae. Record the AE/SAE stop date.
- RECOVERED/RESOLVED WITH SEQUELAE AE/SAE where the subject recuperated but retained pathological conditions resulting from the prior disease or injury.. Record the AE/SAE stop date.
- FATAL A fatal outcome is defined as the SAE that resulted in death. Only the event that was the cause of death should be reported as fatal. AEs/SAEs that were ongoing at the time of death; however, were not the cause of death, will be recorded as "resolved" at the time of death.
- ONGOING (NOT RECOVERED/NOT RESOLVED) An ongoing AE/SAE is defined as an ongoing event with an undetermined outcome.

- An ongoing outcome will require follow-up by the site in order to determine the final outcome of the AE/SAE.
- The outcome of an ongoing event at the time of death that was not the cause of death, will be
  updated and recorded as "resolved" with the date of death recorded as the stop date.
- ONGOING (MEDICALLY STABLE) AE/SAE is ongoing, but medically stable. For example,
   a chronic condition where no further change is expected.

692 If any reported adverse events are ongoing when a participant completes the study (or withdraws),

adverse events classified as UADEs or related SAEs will be followed until they are either resolved, or have no prospect of improvement or change, even after the participant has completed all applicable study visits/contacts. For all other adverse events, data collection will end at the time the participant completes the study. Note: participants should continue to receive appropriate medical care for an adverse event after their participation in the study ends.

If a participant is lost to follow up and participant outcome cannot be determined, outcome classificationwill be the last known outcome.

# 700 **6.3 Reportable Device Issues**

All UADEs and ADEs as defined in section 6.2.1 will be reported on both a Device Issue CRF and AE CRF, except for skin reactions from CGM sensor placement or pump infusion set placement that do not

703 require pharmacologic treatment.

Device complaints and device malfunctions will be reported except in the following circumstances. These
 occurrences are expected and will not be reported on a Device Issue CRF assuming criteria for a UADE
 or ADE have not been met:

- CGM sensor lasting fewer days than expected per manufacturer
- CGM tape adherence issues
- Pump infusion set insertion lasting fewer days than expected per manufacturer
- Battery lifespan deficiency due to inadequate charging or extensive wireless communication
- Intermittent device component disconnections/communication failures not requiring system
   replacement or workaround/resolution not specified in user guide/manual.
- Device issues clearly addressed in the user guide manual that do not require additional troubleshooting

715 Use error (as defined above) will only be reported on a device issue form if an Adverse Event results from 716 the error. In these cases, both a Device Issue and an Adverse Event form will be completed.

717 **6.4 Timing of Event Reporting** 

SAEs possibly related to a study device or procedure and UADEs must be reported by the investigator to the Sponsor within twenty-four (24) hours of the site becoming aware of the event. This can occur via phone or email, or by completion of the AE CRF and Device Issue CRF if applicable. If the AE CRF is not initially completed, it should be completed as soon as possible after there is sufficient information to evaluate the event. All other reportable ADEs and other reportable AEs should be submitted by completion on the respective CRF within seven (7) days of the site becoming aware of the event.

The Sponsor will notify all participating investigators of any adverse event that is serious, related, and unexpected. Notification will be made within ten (10) working days after the Sponsor becomes aware of the event.

- Each site principal investigator is responsible for reporting serious study-related adverse events and
- abiding by any other reporting requirements specific to his/her Institutional Review Board or Ethics
- 729 Committee. Where the JCHR IRB is the overseeing IRB, sites must report all serious, related adverse
- rain events within seven calendar days.
- 731 Upon receipt of a qualifying event, the Sponsor will investigate the event to determine if a UADE has
- occurred, and if indicated, report the results of the investigation to all overseeing IRBs, and the FDA
- within ten (10) working days of the Sponsor becoming aware of the UADE per 21CFR 812.46(b) (2). The
- 734 Sponsor in conjunction with the Medical Monitor must determine if the UADE presents an unreasonable
- risk to participants. If so, the Sponsor must ensure that all investigations, or parts of investigations
- presenting that risk, are terminated as soon as possible but no later than five (5) working days after the Sponsor makes this determination and no later than fifteen (15) working days after first receipt notice of
- the UADE. The investigator(s) may then be required to provide approval or acknowledgment of receipt of
- that notification, and must submit to their overseeing IRB as required.
- 740 The investigators are also required to report, without unjustified delay, all reportable device deficiencies
- that could have led to a UADE, including device deficiencies, irrespective of whether an adverse event
- 742 occurred.

